9.3. Concomitant Medications

Concomitant medications are coded using the World Health Organization (WHO) drug dictionary for anatomical therapeutic chemical classification (ATC) and preferred drug name. A patient who used multiple medications is counted only once for each ATC and preferred drug name. ATC and preferred drug name within each ATC are sorted alphabetically. Coded concomitant medications are summarized by treatment, WHO ATC class and preferred name. Percentages are based on the number of patients in the safety analysis set. Each summary is ordered by descending order of incidence of ATC class and preferred name within each ATC class. Concomitant medications will be summarized by treatment year and overall.

A concomitant medication is any medication taken at the time of first study treatment or a medication that was started after the start of study drug dosing. Specifically, concomitant medications are medications

- that are continued from screening and continued after the first study drug dosing, or
- that have start dates or stop dates within the treatment period, or
- that start before treatment end and have no end date.

Medications with an end date on the date of first study drug administration are not considered concomitant medications. Patients who take excluded medications (defined in the Protocol Section 9.3.1) during the study are listed.

9.3.1. Missing and Partial Concomitant and Other Medication Start and Stop Dates

Missing and partial concomitant medication start and stop dates are detailed in Section 6.6.2.

9.4. Prior and Concomitant Procedures and Surgeries

Prior and concomitant procedures and surgeries are listed.

9.5. Clinical Laboratory Evaluations

Laboratory data are summarized at baseline and at each time point by treatment.

9.5.1. Continuous Summaries of Laboratory Results

Laboratory evaluations and change from baseline are summarized by treatment, laboratory category (hematology, chemistry, urinalysis, and microscopy), test, and study visit using continuous statistics. The eGFR results are calculated using formulas described in Section 6.5.4.

Chemistry values (including eGFR) collected at the following visits will be averaged.

- Week 104 A and Week 104 B
- Week 108 A and Week 108 B
- Week 112 A and Week 112 B

Box plots and line graphs are generated for selected laboratory test results, such as eGFR, ACR, alanine aminotransferase (ALT), aspartate aminotransferase (AST), TBL, BNP, blood urea nitrogen, uric acid, magnesium, creatinine, and creatine kinase (CK). Line graphs include mean \pm SE over time for both the observed values and for change from baseline.

Summaries of continuous statistics are provided for the following urinalysis parameters: albumin, creatinine, pH, erythrocytes, and specific gravity. Qualitative lab results are included in the listings but are not summarized. Laboratory results that are above or below normal limits are flagged in the listings. Summaries of ACR (Section 6.5.5) will use the geometric mean (with standard error) with 95% confidence intervals instead of the arithmetic mean and will display ACR results in original units of mg/g. Changes from baseline in ACR are calculated as the ratio of each visit to baseline and reported as the post-baseline/baseline ratios and are summarized by geometric means with 95% confidence intervals at each time point.

9.5.1.1. Natural log (ACR)/eGFR

Mean ratios of natural log (ACR)/eGFR (Section 6.4.6) are summarized at each time point. The ratio of natural log (ACR)/eGFR by analysis visit is summarized by arithmetic means.

9.5.2. Categorical Summaries of Laboratory Results

Select laboratory parameters will be summarized using shift tables. Shift tables are summarized by treatment, laboratory category (hematology, chemistry, urinalysis, and microscopy), and laboratory test and present shifts from baseline status (Normal, Low, High) to worst on study treatment status (Normal, Low, High). The worst abnormality values are defined as the maximum values while on study treatment (i.e., up to <21 days after last dose), with the exception of magnesium and hemoglobin. The worst abnormal values for magnesium and hemoglobin are defined as the minimum values while on study treatment (i.e., up to <21 days after last dose).

Additionally, laboratory parameters of specific interest (ALT, AST, ACR, BNP) are summarized using shift tables that summarize shifts from (1) baseline status to end of treatment status, (2) worst on-treatment status to worst off-treatment status, (3) worst on-treatment status to end of study, and (4) baseline status to worst on-treatment status 5) baseline to worst off-treatment, and (6) worst on-treatment status to best (lowest) off-treatment status. The number and percentage of patients are summarized. For ACR, summaries will present shifts from/to the categories listed in Section 6.5.5.1. For ALT and AST, summaries will present shifts from/to the following categories:

- \leq ULN
- $>$ ULN to $<3 \times$ ULN
- $\geq 3 \times$ ULN to $<5 \times$ ULN
- $\geq 5 \times$ ULN to $<10 \times$ ULN
- $\geq 10 \times$ ULN to $<20 \times$ ULN
- $\geq 20 \times$ ULN

For BNP, summaries will present shifts from/to the following categories:

- <100 pg/mL
- ≥ 100 pg/ml to <200 pg/ml
- ≥ 200 pg/ml to <400 pg/ml
- ≥ 400 pg/ml

In addition, a summary table is provided for the number and percentage of patients meeting a following pre-specified threshold level at any time during the study:

- ACR >3500 mg/g
- Magnesium <1.3 mEq/L (0.65 mmol/L)
- BNP >200 pg/mL
- NT-proBNP >1000 pg/mL

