#### **9.10.19. Clinical Chemistry**

Samples will be collected for the following clinical chemistry analyses as indicated in Table 4: ferritin, creatine kinase (CK), BUN, enzymatic creatinine, eGFR, TBL, direct bilirubin, ALT, AST, ALP, sodium, potassium, calcium, phosphorus, uric acid, total protein, glucose, albumin, lactate dehydrogenase (LDH), magnesium, chloride, bicarbonate, and GGT.

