**9.10.22. Hematology**

Samples will be collected for the following hematology assessments as indicated in Table 4: hematocrit, hemoglobin, red blood cell (RBC) count, white blood cell (WBC) count, neutrophils, bands (if detected), lymphocytes, monocytes, basophils (if detected), eosinophils (if detected), absolute platelet count, mean corpuscular hemoglobin (MCH), mean corpuscular volume (MCV), and mean corpuscular hemoglobin concentration (MCHC).

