4. STUDY DESIGN

4.1. Summary of Study Design

This international, multi-center, randomized, double-blind, placebo-controlled Phase 3 trial will study the safety, tolerability, and efficacy of bardoxolone methyl in qualified patients with ADPKD. Approximately 850 patients will be enrolled.

Patients will be randomized 1:1 to either bardoxolone methyl or placebo. Randomization will be stratified by eligibility eGFR category (30 to <60; ≥ 60 to 90), concomitant tolvaptan use (yes, no), and screening albumin to creatinine ratio (ACR; ≤ 300 mg/g, >300 mg/g). Patients randomized to placebo will remain on placebo throughout the study, undergoing sham titration. Patients with eGFR 60 to 90 mL/min/1.73 m² at screening should not comprise more than approximately 40% of enrolled patients.

The maximum bardoxolone methyl dose will be determined by baseline proteinuria status. Patients with baseline ACR ≤ 300 mg/g will be titrated to a maximum dose of 20 mg, and patients with baseline ACR >300 mg/g will be titrated to a maximum dose of 30 mg. Patients receiving bardoxolone methyl will start with once-daily dosing at 5 mg and will dose-escalate to 10 mg at Week 2, to 20 mg at Week 4, and then to 30 mg at Week 6 (only if baseline ACR >300 mg/g) unless contraindicated clinically and approved by the medical monitor. Dose de-escalation is permitted during the study if indicated clinically, and subsequent dose re-escalation is also permitted to meet the dosing objective of the highest tolerated dose.

[figure not shown]
All patients in the study will follow the same visit and assessment schedule. Following randomization on Day 1, patients will be scheduled to be assessed during treatment at Week 1, 2, 4, 6, 8, 12, 24, 36, 48, 52, 64, 76, 88, and 100 and by telephone contact on Day 3, 10, 21, 31, 38, and 45. Patients will continue study drug treatment through Week 100. Patients will also be scheduled to be assessed at an in-person follow-up visit at Weeks 103, 104, 108, and 112, after the end of treatment, respectively. The Data Monitoring Committee performs quarterly reviews of unblinded data for safety throughout the study.

Efficacy endpoints will be analyzed after all enrolled patients have completed the study and the final database lock.

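### The laboratory shift tables take the maximum as the worst on-treatment value for every selected analyte except magnesium and hemoglobin, so their Low column under-counts wherever a low value matters

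*SAP*

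**What the plan says.** SAP 9.5.2 opens with "Select laboratory parameters will be summarized using shift tables" and does not name the parameters. The tables are organised by treatment, by laboratory category (hematology, chemistry, urinalysis and microscopy) and by test, and they "present shifts from baseline status (Normal, Low, High) to worst on study treatment status (Normal, Low, High". The direction of worst is then set for all of them: "The worst abnormality values are defined as the maximum values while on study treatment", where on treatment runs to less than 21 days after the last dose. The exception is "The worst abnormal values for magnesium and hemoglobin are defined as the minimum values while on study treatment".

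The same section adds further shift tables for ALT, AST, ACR and BNP, and threshold counts for ACR, magnesium, BNP and NT-proBNP. Magnesium is the only threshold in the low direction.

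The analytes at issue are all collected. Protocol 9.10.19 lists "sodium, potassium, calcium, phosphorus, uric acid, total protein, glucose, albumin, lactate dehydrogenase (LDH), magnesium, chloride, bicarbonate, and GGT" among the chemistry tests, and Protocol 9.10.22 lists "white blood cell (WBC) count, neutrophils, bands (if detected), lymphocytes, monocytes, basophils (if detected), eosinophils (if detected), absolute platelet count" among the hematology tests.

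**The concern.** A table with a Low category needs a rule that can put a patient there. Under the maximum rule, the value used to classify a patient for an analyte where falls are the worry is that patient's most favourable value. The SAP recognises the point for magnesium and hemoglobin. For blood pressure, SAP 9.7 counts both the largest increase and the largest decrease. The laboratory rule does neither for the remaining analytes.

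The Protocol shows that low values of several of these analytes matter to the investigators. Eligibility sets floors for neutrophils and platelets (8.1). Low serum albumin is an exclusion (8.2), and a normal albumin is among the conditions for restarting after a transaminase interruption (9.1.2, Table 5). The muscle spasm guidance (9.1.3) points to magnesium, calcium and potassium as possibly needing replacement. Of those three, only magnesium gets the minimum.

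What is at stake is the display that a safety reader would use to see, by arm, how many patients moved from normal to low. As written, it would show few or none even if many had done so.

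**Working it through.** The SAP gives no figure to reproduce here, so the check applies its rule directly.

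**Number of samples.** From the schedule of assessments (SAP Table 2), post-baseline on-treatment hematology is drawn at Weeks 2, 4, 6 and 8 (4 samples) and at Weeks 12, 24, 36, 48, 52, 64, 76, 88 and 100 (9 samples): 4 + 9 = 13. Chemistry adds Week 1: 13 + 1 = 14. This matches SAP 4.1, where patients are "assessed during treatment at Week 1, 2, 4, 6, 8, 12, 24, 36, 48, 52, 64, 76, 88, and 100" (14 visits). Patients who completed Week 52 before consenting to protocol version 6 are treated as off treatment at that visit (SAP 6.5.2). If it is left out, the counts are 12 and 13. Unscheduled samples would add to them.

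**The rule.** Let LLN be the lower limit of normal. Status is the category of max(x1, ..., xk). The maximum is below LLN only if every xi is below LLN. So Low requires k of k low values, whatever the distribution. Under the minimum, Low requires at least one.

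**Applied to 13 hematology samples**, with the remaining values in range:

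| Low values out of 13 | Status by maximum (SAP) | Status by minimum |
|---|---|---|
| 1 | Normal | Low |
| 3 | Normal | Low |
| 6 | Normal | Low |
| 12 | Normal | Low |
| 13 | Low | Low |

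**Dependence on follow-up.** A patient with a single on-treatment sample that is low is tabulated as Low. A patient low at 12 of 13 is tabulated as Normal.

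**Illustration with correlated values.** The inputs are assumptions and none comes from the documents: a standardised analyte with normal limits at ±1.96, between-patient SD 0.8 with the patient's usual level held within ±1.5, within-patient SD 0.5, 13 visits, and a fall starting at a random visit. Among patients with at least one low value, the maximum rule records:

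| Fall | Low | Normal | High |
|---|---|---|---|
| 2 SD, 1 visit | 0.0% | 99.6% | 0.4% |
| 4 SD, 1 visit | 0.0% | 91.8% | 8.2% |
| 2 SD, 3 visits | 0.0% | 99.4% | 0.6% |
| 4 SD, 3 visits | 0.0% | 92.1% | 7.9% |
| 2 SD, sustained to the end | 1.9% | 97.6% | 0.5% |
| 4 SD, sustained to the end | 7.2% | 87.7% | 5.2% |

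The 7.2% is close to 1/13 = 7.7%, the share of patients whose fall starts at the first visit. A later fall leaves at least one earlier value that is normally in range. The percentages move with the assumptions, but the k-of-k condition does not.

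**Where else low values appear.** By-visit continuous summaries (SAP 9.5.1) include the first quartile and minimum by default (SAP 6.2). They show the lower tail at each visit but not how many patients crossed a limit. Listings carry a flag: "Laboratory results that are above or below normal limits are flagged in the listings". They give no count by arm. Clinically significant abnormalities can be reported as adverse events (Protocol 11.2.1.1 and 11.6) and are then tabulated (SAP 9.1.2).

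**The case against.** The strongest reply is about scope. The tables cover selected parameters that the SAP does not list, so it cannot be said that platelets, neutrophils, albumin or potassium will be tabulated at all. That stands, and the point is conditional on selection. Hematology and chemistry are named as categories, however, and the rule governs whatever is chosen from them.

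Second, this is one descriptive display. Statistical testing of safety data is not planned unless otherwise specified (SAP 9), and the data monitoring committee reviews unblinded safety data during the trial (Protocol 9.6.3). Low values also reach the by-visit summaries, the listings and the adverse event tables. A reader might infer that falls would be lost, or that a difference between arms would be missed. The documents do not support that. What is missing is a patient count by arm.

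Third, some examples are weaker than others. For potassium, the Protocol names hyperkalemia (9.1.7), which the maximum captures. Only the low side is affected, and 9.1.3 gives the reason to look at it. A reader might also extend the rule to eGFR. The SAP does not name eGFR as selected for these tables and gives no Normal/Low/High range for it.

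Finally, full follow-up will not be universal. Sites were told on 10 May 2023 that development was stopping (SAP 2), so some patients will have fewer than 13 or 14 samples. That makes the Low category easier to reach for them, but it also makes the column depend on exposure.

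**Conclusion.** The point holds for the shift tables. For every selected analyte other than magnesium and hemoglobin, Low is reached only when all on-treatment values are low: 13 of 13 scheduled hematology samples or 14 of 14 chemistry samples with full follow-up, and fewer with shorter treatment. Wherever a low value matters, the Low column under-counts and varies with the number of samples. This follows from the stated definition and needs no assumption about rates.

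It would go too far to say that all harmful falls are recorded as normal. A patient low throughout is recorded as Low, a patient with any high value is recorded as High, and selection of a given analyte is not confirmed. Nor does the point touch an endpoint or a decision rule. It should still be corrected, because no laboratory table in the readable text supplies the missing count. Only magnesium, by the minimum rule and its threshold, and hemoglobin, by the minimum rule if selected, are covered. Parts of the SAP are blacked out, so this last statement is limited to what can be read.

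**What to change.** In SAP 9.5.2, name the selected parameters. For each one with a two-sided reference range, report two shifts: baseline to lowest on-treatment value and baseline to highest on-treatment value. At minimum, state the direction of concern for each parameter and use the minimum where that direction is low. Showing the number of on-treatment samples per patient by arm beside the tables would help in reading them, since any extreme-value count grows with the number of samples.

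The cost is one SAP sentence, a short parameter list and an extra column block per table. No new data are needed and no clinical rule changes.

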Clinical Chemistry (incl. eGFR) ^k	X	X	X	X	X	X	X
BNP and NT-proBNP			X		X		
Hemoglobin A1c							
Hematology			X		X		
Coagulation			X		X		
Basic Lipid Panel			X		X		
Urinalysis and Microscopy			X		X		
Urine Collection for ACR ^l			X		X		
Virus Serology							
PK Samples ^m	X		X		X		
SARS-CoV-2 Antibody Test					X		
Ambulatory Blood Pressure Monitoring ^o							
Tanner Staging ^q					X		

Abbreviations: ABPM = ambulatory blood pressure monitoring, ACR = albumin to creatinine ratio, ADPKD = autosomal dominant polycystic kidney disease, AE = adverse event, BNP = B-type natriuretic peptide, ██████████, ECG = electrocardiogram, eGFR = estimated glomerular filtration rate, IRB/EC = institutional review board/ethics committee, IWRS = Interactive Web Response System, NT-proBNP = N-terminal pro-brain natriuretic peptide, ██████████

██████████, PK = pharmacokinetic, SARS-CoV-2 = Severe Acute Respiratory Syndrome Coronavirus 2, Wk = week, WOCBP = women of child-bearing potential

-
- ^a Total Screening period should not exceed 90 days.
- ^b Screen B visit should be at least 1 day after Screen A and no more than 30 days prior to Day 1.
- ^c Day 1 should be the day of randomization and administration of the first dose. Where randomization in the IWRS must occur earlier than Day 1, the Day 1 visit must align with the administration of the first dose. **On Day 1, all procedures must be performed before study drug administration.**
- ^d Screening eligibility procedures do not need to be repeated on Day 1; however, a review of any changes in eligibility criteria should be evaluated prior to Day 1 procedures
- ^e Height will be recorded in centimeters. Adult patients (18≤age≤70 years at Screen A visit) will be measured at Screen A only. Adolescent patients (12≤age<18 years at Screen A visit) will be measured at all specified timepoints.
- ^f An echocardiogram performed during screening or within 6 months prior to Day 1 may be used to determine eligibility.
- ^g Screen B vital sign measurements are needed only if re-assessing blood pressure for eligibility.
- ^h A serum pregnancy test will be performed at the Screen A visit for WOCBP or at any point in time if a pregnancy is suspected. All other pregnancy assessments will be urine pregnancy tests. Additional pregnancy assessments will be performed more frequently if required by local law or requested by local regulatory authorities or IRBs/ECs.

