6.5.2. Visit Windows

Analysis visits and their windows are defined using derived study day (Section 6.5.1) instead of relying on visit labels in the clinical database because clinical visits may occur outside protocol-specified windows. Study day and days after last dose are calculated using the actual date of each scheduled and unscheduled assessment and compared to the target for each analysis visit as specified in Table 4 and Table 5. They are included in analyses of safety and efficacy as follows:

- Efficacy analyses for endpoints assessed through Week 100 use the analysis windows in Table 4, irrespective of whether or not a patient is receiving treatment of study drug.
- Efficacy analyses for endpoints assessed during the follow-up period after Week 100 use the analysis window in Table 4 irrespective of how long a patient has been off-treatment.
- Protocol version 6 eliminated the off-treatment period from Week 48 to Week 52. Patients completing the Week 52 visit prior to consenting to protocol version 6 will be considered “off-treatment” at Week 52. All other patients are expected to be on-treatment at Week 52. Week 52 analysis values in Table 4 will not be used in the efficacy analyses unless otherwise specified. Week 52 values are only summarized descriptively because of the mix of on-treatment and off-treatment values.
- Safety analyses use the analysis windows defined in Table 4 so long as the patient is receiving treatment of study drug. Once a patient permanently discontinues study treatment, safety data are summarized according to time since last dose as defined in Table 5.

Unless otherwise specified if a parameter is assessed or measured more than once within a visit window, the one that is closest to the protocol-scheduled time point (i.e., target) is used for the purposes of data analysis and summary.

If 2 assessments are equidistant from a target, the earlier assessment is used. If 2 assessments are on the same day, the average of 2 assessments will be used for non-laboratory parameters. For laboratory parameters, if both an original and retest result are available in the laboratory dataset, the original result will be used and the second (i.e., “retested”) result will be ignored.

One exception is that 2 scheduled chemistry values (including eGFR) are collected within the Week 52 (prior to protocol version 6), Week 104, Week 108, and Week 112 analysis windows.

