6.5.2.1. Off-Treatment Visit Windows Relative to Last Dose for Safety

Patients who permanently discontinue study drug prior to Week 100 are asked to resume the planned assessments according to the study schedule in the protocol. Off-treatment values for clinical laboratory evaluations (Section 9.5), vital signs (Section 9.7), and electrocardiograms (Section 9.9) are those that occur after the last dose date for patients permanently discontinuing study drug prior to Week 100, and are summarized relative to their last dose of study drug. Off-treatment safety assessments (clinical labs, vital signs, and ECGs) are grouped for analyses according to the strategy in Table 5. Assessments that occur on or before the date of last dose through 20 days after last dose are considered on-treatment period.

Table 5: ANALYSIS VISITS FOR OFF-TREATMENT SAFETY FOLLOWING EARLY TREATMENT DISCONTINUATION

Off-Treatment Safety Analysis Visit	Label	Target Study Day (days after last dose)	Analysis Window
0	Last dose (on-treatment) ^a	0	0 (days after last dose ≤20)
4	Off Treatment 4-weeks ^b	28	21 ≤ days after last dose ≤ 35
8	Off Treatment 8-weeks ^b	56	36 ≤ days after last dose ≤ 71
12	Off Treatment 12-weeks ^b	84	72 ≤ days after last dose ≤ 99
24	Off Treatment 24-weeks ^b	168	100 ≤ days after last dose ≤ 252
48	Off Treatment 48-weeks ^b	336	253 ≤ days after last dose ≤ 350
72	Off Treatment 72-weeks ^b	504	351 ≤ days after last dose ≤ 518
96	Off Treatment 96-weeks ^b	672	519 ≤ days after last dose ≤ 686

^a Last dose for patients permanently discontinuing study drug prior to Week 100. Assessments that occur on the date of last dose or less than 21 days after last dose are considered on treatment and summarized using Table 4 windows.

^b The off-treatment values indicate the value closest to the date of last dose and at least 21 days after last dose.

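### Within an arm, SAP 9.5.2 shift tables (3) and (6) show recovery off drug even when nothing changed, and table (2) moves in a direction set by the number of values

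*SAP*

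**What the plan says.** SAP 9.5.2 singles out ALT, AST, ACR and BNP for six shift tables. Tables (1), (4) and (5) start from baseline. The other three start from the worst on-treatment status: "2) worst on-treatment status to worst off-treatment status, (3) worst on-treatment status to end of study", and "6) worst on-treatment status to best (lowest) off-treatment status". For these parameters worst means highest: "The worst abnormality values are defined as the maximum values while on study treatment (i.e., up to <21 days after last dose". ALT and AST use six multiples-of-ULN categories, BNP is cut at 100, 200 and 400 pg/mL, and ACR at 300 mg/g.

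The number of values comes from the schedule (SAP Table 2, protocol Table 4). Patients are "assessed during treatment at Week 1, 2, 4, 6, 8, 12, 24, 36, 48, 52, 64, 76, 88, and 100", which is 14 visits, with chemistry and BNP at each. The row "Urine Collection for ACR" is marked at 11 of them (not Weeks 1, 2 or 6). Off treatment, chemistry is drawn at all seven visits; SAP 6.5.2 confirms that "2 scheduled chemistry values (including eGFR) are collected within the Week 52 (prior to protocol version 6), Week 104, Week 108, and Week 112". The rows "BNP and NT-proBNP" and ACR are marked only at Weeks 104B and 108B.

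For early stoppers, SAP 6.5.2.1 states: "Patients who permanently discontinue study drug prior to Week 100 are asked to resume the planned assessments according to the study schedule in the protocol". Nothing in 9.5.2 equalises the number of on-drug and off-drug values or warns how these tables should be read.

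**The concern.** The maximum of many readings lies above a patient's usual level by chance. Set against one later reading, or against the lowest of several, it falls even if the patient's true level never moved. A reader who looks down the bardoxolone column of table (3) or (6) would then see reversal after withdrawal where there may be none.

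The question is a live one for this drug. Protocol 5.1.2.6 attributes rises in urinary albumin to pharmacology and not to injury, and protocol 5.1.2.2 describes transaminase rises as self-limiting. The six tables are the planned categorical view of these parameters, and none goes from end-of-treatment status to a fixed off-treatment visit, which is the direct test of reversal.

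**Working it through.** The plan gives no figure for these tables, so there is none to reproduce. The check has four parts.

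**1. Counts for a patient treated to Week 100.** ALT/AST: 14 on, 7 off (4 analysis values if A/B pairs are averaged). BNP: 14 on, 2 off. ACR: 11 on, 2 off.

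**2. Expected shift with no true change.** Let m(n) be the expected maximum of n independent standard normal values. In within-patient SDs the expected shift is m(off) - m(on) for table (2), -m(on) for table (3), and -m(off) - m(on) for table (6). By simulation m(2) = 0.565, m(7) = 1.353, m(11) = 1.587, m(14) = 1.704.

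| | Table (2) | Table (3) | Table (6) |
|---|---|---|---|
| ALT/AST, 14 v 7 | 1.353 - 1.704 = -0.35 | -1.70 | -1.353 - 1.704 = -3.06 |
| BNP, 14 v 2 | 0.565 - 1.704 = -1.14 | -1.70 | -0.565 - 1.704 = -2.27 |
| ACR, 11 v 2 | 0.565 - 1.587 = -1.02 | -1.59 | -0.565 - 1.587 = -2.15 |

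With A/B averaging, ALT/AST become -0.89, -1.70 and -2.51. The signs for tables (3) and (6) hold whenever there is more than one on-drug value. The sign for table (2) follows the counts.

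**3. Category shifts with no true change (200,000 simulated patients per scenario).** The documents give no spreads, so these are assumptions on the log scale. ALT: median 0.5 x ULN, between-patient SD 0.35, within-patient SD 0.2-0.4. BNP: median 25 pg/mL, 0.8, 0.3-0.7. ACR: median 60 mg/g, 1.3, 0.3-0.7. The SAP cut-points are used. Percent of all patients improving / worsening at the middle within-patient SD:

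| | Table (2) | Table (3) | Table (6) | Last on v last off |
|---|---|---|---|---|
| ALT | 13.5 / 5.2 | 26.1 / 0.9 | 31.5 / 0.0 | 4.5 / 4.5 |
| BNP | 20.4 / 1.7 | 22.9 / 0.9 | 25.5 / 0.0 | 4.5 / 4.5 |
| ACR | 11.3 / 1.0 | 15.0 / 0.5 | 18.7 / 0.0 | 4.1 / 4.1 |

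Over the assumed range, false improvement in table (6) is 16-48% for ALT, 13-40% for BNP and 11-28% for ACR. With an ACR geometric mean of 40 mg/g and within-patient SD 0.3, 12% have a worst value above 300, and 59% of those are at or below 300 at their lowest off-drug value: 0.12 x 0.59 = 7%. The ACR range is therefore 7-28%. Worsening in table (6) is 0.1% or less for these patients.

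**4. Where table (2) and the placebo column behave differently.**

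- *Stop at Week 12, followed to Week 112.* On drug: 6 ALT and BNP values, 3 ACR values. Off drug: 8 regular visits (Weeks 24 to 100) plus 7 chemistry draws = 15 for ALT. For BNP and ACR it is 8 + 2 = 10, or up to 12 with the visits added after early stopping; 11 was used. Table (2) improve / worsen: ALT 4.3 / 15.5, BNP 5.5 / 12.2, ACR 1.5 / 9.4. This is apparent worsening with no change.
- *Stop at Week 24 with 12 weeks off drug.* ALT has 7 v 7 values and no net shift in table (2) (8.4 / 8.5). BNP (7 v 2) gives 14.1 / 2.9 and ACR (4 v 2) gives 6.7 / 2.6.
- *ALT with an early rise.* Assume a doubling at Weeks 4-8 on drug, fully resolved before withdrawal, and no change off drug (within-patient SD 0.3). Table (6) shows 73% improving on drug and 31% on placebo; table (3) shows 67% and 26%. Last on v last off gives about 4.5% each way in both arms.

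**The case against.** The strongest reply is that placebo already stands beside drug. The tables are by treatment, placebo patients undergo sham titration on the same schedule, and chance regression affects both columns alike. This stands for the chance part, provided drug duration, and hence the counts, are similar in the two arms. It fails for transaminases. Protocol 5.1.2.2 says the rises peak about two to four weeks after starting or raising the dose and mostly resolve while drug continues. That resolution occurs in the drug arm only, and tables (3) and (6) would show it as change after withdrawal.

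It is also fair that safety data are untested by default (SAP 9), that SAP 9.5.1 gives values and changes at every visit with plots for these parameters, and that a worst-value table usefully shows whether a peak came down. These points limit the harm and argue against simply discarding every such table. They do not make tables (3) and (6) a measure of reversal.

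Two stronger readings are tempting. A reader might infer that all three tables always show false recovery off a handful of off-drug values. The documents do not support that: table (2) compares two maxima, ALT and AST have seven off-drug draws, and early stoppers can have more values off drug than on. Study drug was ended for all sites on 10 May 2023 (SAP 2), so unequal counts are likely. A reader might also infer that the sponsor plans to claim reversal from these tables. No passage says so.

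**Conclusion.** The concern holds for tables (3) and (6) read within an arm: they show improvement with no true change, and table (6) is close to one-directional by construction. That direction needs no assumption beyond several on-drug values and some within-patient variation. The sizes in table (6) rest on assumed medians and spreads and on independent readings, and they apply to patients treated to Week 100. For ALT and AST the drug-placebo contrast is also unsafe as evidence of reversal. Table (2) carries a count artefact of varying sign: false recovery for BNP and ACR in patients treated to Week 100, less for ALT and AST, none at equal counts, and false worsening in early stoppers followed to Week 112. This should be corrected. It touches descriptive safety tables and not the efficacy analysis.

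**What to change.** Add one shift table by treatment arm, from end-of-treatment (last on-treatment) status to a fixed off-treatment visit. For patients treated to Week 100 use Week 108, where chemistry, BNP and ACR are all scheduled. For early stoppers use the 8-week off-treatment window in SAP Table 5. Put it in place of table (6), and name it as the table for any statement about reversal. If tables (2), (3) or (6) are kept to describe resolution of peaks, footnote that they compare selected values from unequal numbers of samples and cannot show reversal after withdrawal. Keep tables (1), (4) and (5).

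The cost is a few lines of SAP text and one simple table program, with no new data. SAP 2 places finalisation before database lock, so the change can be made there. The new table will not show early on-drug peaks; table (4) still does.
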